9.7 Subgroup Analyses

The following endpoints will be analyzed according to the primary estimand by subgroup: Subjects with prior sinus surgery versus without prior sinus surgery at baseline. Further detail on the statistical methods will be provided in the SAP.

- Co-primary endpoints (CSNS, APOV)
- All CSNS endpoints other than the primary,
- All individual daily nasal symptoms scores that are components of the CSNS (as well as sense of smell)
- SNOT-22 total score

9.8 Type I Error Control for Multiplicity

9.8.1 Co-primary Efficacy Endpoints

The primary hypothesis of this trial is that OPN-375 high dose (372 µg) group will be superior to the placebo group in both co-primary endpoints.

The familywise Type 1 error probability for the test of the primary hypothesis is $\alpha=0.05$. The strategy for strong, familywise control of the Type I error is based on closed testing procedure as follows.

1. Test each co-primary endpoint for OPN-375 high dose (372 µg) vs placebo: If $p < 0.05$ for both endpoints, then proceed to key secondary endpoints; otherwise, stop. The order of the testing is as follows:
 - a. OPN-375 372 µg versus placebo in the change from baseline in the 7-day average CSNS (instantaneous AM) at the end of Week 4
 - b. OPN-375 372 µg versus placebo in the APOV in the ethmoid and maxillary sinuses change from baseline to Week 24/ET

9.8.2 Type I Error Control for Key Secondary Endpoints

The following planned comparisons are defined based on pooled data from Study OPN-FLU-CS-3205 and Study OPN-FLU-CS-3206. Testing will continue based on closed testing procedure, with $\alpha=0.05$, if the primary hypothesis is met, as follows:

1. OPN-375 372 µg versus placebo in the frequency of acute exacerbations of CRS over 24 weeks
2. OPN-375 372 µg versus placebo in the frequency of acute exacerbations of CRS over 24 weeks in CRS without NP population
3. OPN-375 372 µg versus placebo in change from baseline to Week 4 on CSNS score in subjects who were symptomatic at trial entry despite reported use of an intranasal steroid for treatment of CRS within 30 days of Visit 1

The following planned comparisons are defined based on Study OPN-FLU-CS-3206. Testing will continue based on closed testing procedure, with $\alpha=0.05$, if the key secondary hypotheses (1-3) are met, as follows:

4. Test each co-primary endpoint for OPN-375 low dose (186 μg) vs placebo: If $p < 0.05$ for both endpoints, then proceed to next endpoints; otherwise, stop. The order of the testing is as follows:
 - a. OPN-375 372 μg versus placebo in the change from baseline in the 7-day average CSNS (instantaneous AM) at the end of Week 4
 - b. OPN-375 372 μg versus placebo in the APOV in the ethmoid and maxillary sinuses change from baseline to Week 24/ET
5. OPN-375 372 μg versus placebo in change from baseline to the end of Week 4 in nasal congestion
6. OPN-375 372 μg versus placebo in change from baseline to the end of Week 4 in nasal discharge (anterior and/or posterior)
7. OPN-375 372 μg versus placebo in change from baseline to the end of Week 4 in facial pain or pressure sensation
8. OPN-375 372 μg versus placebo in change from baseline to the end of Week 4 in sense of smell
9. OPN-375 372 μg versus placebo in time to first acute exacerbation of CRS

The following planned comparisons are defined based on pooled data from Study OPN-FLU-CS-3205 and Study OPN-FLU-CS-3206. Testing will continue based on closed testing procedure, with $\alpha=0.05$, if the primary hypothesis is met, as follows:

10. OPN-375 186 μg versus placebo in the frequency of acute exacerbations of CRS over 24
11. OPN-375 186 μg versus placebo in the frequency of acute exacerbations of CRS over 24 weeks in CRS without NP population
12. OPN-375 186 μg versus placebo in change from baseline to Week 4 on CSNS score in subjects who were symptomatic at trial entry despite reported use of an intranasal steroid for treatment of CRS within 30 days of Visit 1

The following planned comparisons are defined based on Study OPN-FLU-CS-3206. Testing will continue based on closed testing procedure, with $\alpha=0.05$, if the key secondary hypotheses (9-11) are met, as follows:

13. OPN-375 186 μg versus placebo in change from baseline to the end of Week 4 in nasal congestion in CRS without NP population
14. OPN-375 186 μg versus placebo in change from baseline to the end of Week 4 in nasal discharge (anterior and/or posterior)
15. OPN-375 186 μg versus placebo in change from baseline to the end of Week 4 in facial pain or pressure sensation
16. OPN-375 186 μg versus placebo in change from baseline to the end of Week 4 in sense of smell
17. OPN-375 186 μg versus placebo in time to first acute exacerbation of CRS

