9.1 Sample Size Determination

Sample size assumptions were originally generated based on previous Phase 3 studies of OPN-375 in subjects with nasal polyposis and data from a study evaluating the change in maxillary and ethmoid opacification in CRS patients treated with an intramuscular dose of triamcinolone (Pallanch 2013). Updated standard deviation estimates for both co-primary endpoints in this amendment are based on a blinded interim analysis of Protocol OPN-FLU-CS-3205. Based on the results for changes from baseline in morning symptoms among subjects with nasal polyps in the previous studies conducted with OPN-375, a sample of 70 subjects per group (210 total subjects) is sufficient to detect a 0.9 scale difference in 7-day average CSNS (AM instantaneous) between treatments (OPN-375 vs placebo) using a 2-sided test at the 5% significance level with 88% power, and assuming a standard deviation (SD) of 1.7. This sample size is also adequate to detect a 9% difference between treatments in average percent opacification (APOV) using a 2-sided test at the 5% significance level with 88% power, and assuming a SD of 17%. The sample size was estimated for the co-primary efficacy endpoints using Power Analysis and Sample Size Software (PASS 15) (NCSS, 2017).

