2 INTRODUCTION

This Statistical Analysis Plan (SAP) references Protocol OPN-FLU-CS-3206 (Amendment 4.0, dated 11 May 2022) and the corresponding electronic case report form (eCRF). There are no deviations from this amendment presented in this SAP.

Protocol OPN-FLU-CS-3206 is the second of the two pivotal randomized, controlled clinical trials intended to provide substantial evidence supporting an indication for the treatment of CRS, and this study is identical in design to Protocol OPN-FLU-CS-3205 with one important exception. Protocol OPN-FLU-CS-3205 enrolled a subject population including subjects with or without the presence of Nasal Polyps at baseline. Protocol OPN-FLU-CS-3206 included only subjects without Nasal Polyps present at baseline.

In the interest of clarity and efficiency, the OPN-FLU-CS-3205 SAP, (14 February, 2022) is the Statistical Analysis Plan of reference for this clinical program. The OPN-FLU-CS-3205 SAP encompasses the efficacy and safety endpoints, estimand, statistical methods, and data handling rules used in the CRS development program. Thus, the CS-3205 SAP is the primary reference for the statistical analyses of efficacy and safety endpoints, as well as the statistical estimands and methods, endpoint definitions, and data handling rules, unless otherwise indicated in this document.

The focus of this OPN-FLU-CS-3206 SAP is to document changes and additions to secondary endpoints, to highlight the changes to statistical models as a result of no stratification for polyp status, and to specify the hypothesis testing strategy to control the family-wise Type I error probability in study OPN-FLU-CS-3206.

If additional analyses are performed to supplement the planned analyses they will be identified as such in the Clinical Study Report (CSR).

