5.3.2 Type I Error Control for Key Secondary Endpoints

The following planned comparisons are defined based on pooled data from Study OPN-FLU-CS-3205 and Study OPN-FLU-CS-3206. Testing will continue based on closed testing procedure, with $\alpha=0.05$, if the primary hypothesis is met, as follows:

2. OPN-375 372 μg versus placebo in the frequency of acute exacerbations of CRS over 24 weeks
3. OPN-375 372 μg versus placebo in the frequency of acute exacerbations of CRS over 24 weeks in CRS without NP population
4. OPN-375 372 μg versus placebo in change from baseline to Week 4 on CSNS score in subjects who were symptomatic at trial entry despite reported use of an intranasal steroid for treatment of CRS within 30 days of Visit 1

The following planned comparisons are defined based on Study OPN-FLU-CS-3206. Testing will continue based on closed testing procedure, with $\alpha=0.05$, if the key secondary hypotheses (2-4) are met, as follows:

5. Test each co-primary endpoint for OPN-375 low dose (186 μg) vs placebo: If $p < 0.05$ for both endpoints, then proceed to next endpoints; otherwise, stop. The order of the testing is as follows:
 - a) OPN-375 372 μg versus placebo in the change from baseline in the 7-day average instantaneous AM CSNS at the end of Week 4
 - b) OPN-375 372 μg versus placebo in the APOV in the ethmoid and maxillary sinuses change from baseline to Week 24/ET
6. OPN-375 372 μg versus placebo in change from baseline to the end of Week 4 in nasal congestion
7. OPN-375 372 μg versus placebo in change from baseline to the end of Week 4 in nasal discharge (anterior and/or posterior)
8. OPN-375 372 μg versus placebo in change from baseline to the end of Week 4 in facial pain or pressure sensation
9. OPN-375 372 μg versus placebo in change from baseline to the end of Week 4 in sense of smell
10. OPN-375 372 μg versus placebo in time to first acute exacerbation of CRS

The following planned comparisons are defined based on pooled data from Study OPN-FLU-CS-3205 and Study OPN-FLU-CS-3206. Testing will continue based on closed testing procedure, with $\alpha=0.05$, if the key secondary hypotheses (5-10) are met, as follows:

11. OPN-375 186 µg versus placebo in the frequency of acute exacerbations of CRS over 24
12. OPN-375 186 µg versus placebo in the frequency of acute exacerbations of CRS over 24 weeks in CRS without NP population

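### The key-secondary hierarchy names the wrong dose in the 186 µg co-primary step (both documents), and the protocol's gates for the 186 µg tests break the claimed 5% familywise control

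*Protocol*

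**What the plan says.** Protocol section 9.8.1 makes superiority of 372 µg on both co-primary endpoints the primary hypothesis. It then states: "The strategy for strong, familywise control of the Type I error is based on closed testing procedure as follows". The level is 0.05.

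Section 9.8.2 continues with 17 numbered items in five blocks.

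- **Dose label.** Item 4 opens "Test each co-primary endpoint for OPN-375 low dose (186" and requires p < 0.05 on both endpoints, otherwise testing stops. Its sub-items 4a (CSNS) and 4b (APOV) both name 372 µg. SAP section 5.3.2, item 5, has the same heading and the same 372 µg sub-items.
- **Gate for items 10-12** (186 µg, pooled data). The protocol allows these at alpha 0.05 "if the primary hypothesis is met, as follows". The same words open items 1-3.
- **Gate for items 13-17** (186 µg, study 3206). The protocol allows these "if the key secondary hypotheses (9-11) are met, as follows".
- **SAP gates.** The SAP numbers every item one higher. It opens the pooled 186 µg tests "if the key secondary hypotheses (5-10) are met, as follows" and the study-level 186 µg tests once its items 11-13 are met.

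SAP section 2 nevertheless says of protocol amendment 4.0: "There are no deviations from this amendment presented in this SAP".

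**The concern.** The hierarchy decides which dose claims are confirmatory in a trial that the SAP calls pivotal. Three things look wrong.

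1. A step meant to test 186 µg on the co-primary endpoints lists only the 372 µg tests. Nothing after the primary is reached unless those have already succeeded. As listed, 186 µg can go on to collect key secondary claims without its co-primary endpoints being tested, and a 186 µg co-primary claim has no alpha assigned to it.
2. In the protocol, the pooled 186 µg items depend only on the primary hypothesis. Items 1-9 and items 10-12 then form two parallel branches, each at full alpha. That is not a closed or fixed-sequence procedure at 0.05.
3. The gate for items 13-17 includes a 372 µg item (9) and omits item 12, so item 12 can fail and testing still goes on to item 13.

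The documents also diverge. Suppose 372 µg wins both co-primaries but fails item 1, the pooled exacerbation frequency. The protocol still permits a confirmatory 186 µg exacerbation claim. Under the SAP, testing has stopped.

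**Working it through.** **Plan's own figure.** Protocol section 9.1 gives 70 per group, a CSNS difference of 0.9 with SD 1.7, an APOV difference of 9% with SD 17%, and a two-sided 5% test. The standardized effect is 0.9/1.7 = 9/17 = 0.529. Multiplied by √(70/2) = 5.916, this gives 3.132, so power = Φ(3.132 − 1.960) = 87.9% (87.5% with the noncentral t). The stated 88% reproduces.

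**Gates side by side.**

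| Block | Protocol items: condition | SAP items: condition | SAP condition in protocol numbering |
|---|---|---|---|
| 372 µg, pooled | 1-3: primary | 2-4: primary | primary |
| Headed 186 µg co-primary, lists 372 µg | 4: items 1-3 | 5: items 2-4 | 1-3 |
| 372 µg, study 3206 | 5-9: item 4 | 6-10: item 5 | 4 |
| 186 µg, pooled | 10-12: **primary only** | 11-13: items 5-10 | 4-9 |
| 186 µg, study 3206 | 13-17: **items 9-11** | 14-18: items 11-13 | 10-12 |

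The SAP is one fixed sequence. The protocol is not.

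**The listed co-primary step.** Items 4a/4b repeat tests already passed, so the step passes with probability 1 once reached. If it tested 186 µg and that dose had no effect on either co-primary, with the two endpoints taken as independent, it would pass with probability 0.05² = 0.0025 (simulated 0.0026).

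**Protocol gate for items 10-12.** Take the primary as met and items 1 and 10 as both null. Each is tested at two-sided 0.05, so

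familywise error = 1 − P(|Z₁| < 1.96, |Z₂| < 1.96).

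With equal arms sharing one placebo group, the correlation of the two statistics is (1/n)/(2/n) = 0.5. Protocol section 2.5 gives 1:1:1 for this study. The allocation in study 3205 is not in these documents, so a range is shown.

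| Correlation | Familywise error |
|---|---|
| 0 | 1 − 0.95² = 0.0975 |
| 0.5 | 0.0907 |
| 0.7 | 0.0835 |
| 0.9 | 0.0704 |

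The Bonferroni bound is 0.05 + 0.05 = 0.10. Counting only errors in favour of the drug, the figure is 0.045 at correlation 0.5 and 0.049 at 0, against 0.025.

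**Simulation of both hierarchies as written** (400,000 runs per scenario, different endpoints taken as independent):

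| Scenario | Protocol gates | SAP gates |
|---|---|---|
| Primary met, all key secondaries null | 0.091 | 0.050 |
| Only items 9 and 10 null | 0.097 | 0.050 |
| Only items 12 and 13 null (the 9-11 gate) | 0.097 | 0.050 |
| 372 µg co-primaries at the planned effect, all key secondaries null | 0.070 | 0.038 |

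The last row follows by hand: 0.879² × 0.0907 = 0.070. In the third row the two tests share subjects and related scores, and the documents do not give their correlation. The correlation table above shows the effect of a positive value: the error falls but stays above 0.05.

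**The case against.** The strongest reply is that the intent is visible. The lead sentence of item 4 is a complete instruction to test 186 µg, and the sub-items look like a copy of the primary step. Consecutive numbering, the statement that testing continues, the stop rule in item 4 and a 9-11 gate that looks one off all suggest a single sequence. The SAP, one of whose stated purposes is to set the testing strategy, has serial gates that hold 5% even with 372 µg left in item 5. The dose label therefore does not itself inflate error over the listed hypotheses. Finally, 9.1% assumes that the primary succeeds; at the planned effects the figure is 7.0%.

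Much of this stands as a limit on scope. The inflation belongs to the protocol's gates and not to the SAP's. If the lead sentence of item 4/5 governs, the SAP does not let 186 µg bypass its co-primaries, and under the protocol only items 10-12 escape that step, because items 13-17 need item 9.

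It does not remove the defect. The protocol's stated condition for items 10-12 contradicts the serial reading and its own stop rule. Strong control must hold under every configuration of true and false nulls, so the worst case is the right test, and 7.0% is also above 5%. The SAP cannot settle the dose label because it carries the same error. Neither document says which prevails.

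**Conclusion.** The concern holds. As listed in both documents, the 186 µg co-primary step is an empty gate, and 186 µg versus placebo on CSNS and APOV is not among the listed comparisons. This leaves a 186 µg co-primary claim outside the controlled family; it does not by itself raise the error rate.

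The protocol's literal gates do raise it: 9.1% at correlation 0.5, with 8.35% to 9.75% for correlations from 0.7 down to 0, against the claimed 5%. These figures are conditional on the primary being met and the two branch hypotheses being null. With the 372 µg co-primaries at their planned effect, independent of each other, and all key secondaries null, it is 7.0%. The gate on items 9-11 gives 9.7% if items 12 and 13 are the only nulls and their statistics are independent, and less if they are positively correlated.

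The SAP's gates hold 5% over the hypotheses they list, but they differ from the protocol's, so the SAP's statement that it contains no deviations is inaccurate. This must be corrected because it changes which dose claims are confirmatory.

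**What to change.** - In protocol section 9.8.2 items 4a and 4b, and SAP section 5.3.2 items 5a and 5b, replace 372 µg with 186 µg, in line with the heading of the step.
- In protocol section 9.8.2, make items 10-12 conditional on items 4-9 being met, and items 13-17 conditional on items 10-12. Both documents then give the SAP's single fixed sequence, with familywise error of at most 0.05 and the 186 µg co-primaries ahead of every 186 µg secondary claim.
- Re-check the SAP's no-deviation statement against the corrected protocol.

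The cost is a few words in the SAP and a protocol clarification, with no change to data collection or sample size. Make the change before the treatment codes are unblinded; made later, the choice of sequence could be seen as driven by the results.

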9.9 Safety Analysis

All safety summaries will be descriptive; no statistical inference procedures will be applied. All safety summaries will be presented by OPN-375 dose level 186 µg, 372 µg, and OPN-375 combined doses and placebo.

9.9.1 Adverse Events (AEs)

All reported AEs will be coded using the Medical Dictionary for Regulatory Activities (MedDRA) version 20 or higher. Treatment emergent AEs (TEAEs) are defined as AEs with onset dates on or after the start of double-blind study drug. The incidence of TEAEs during the study period will be tabulated by treatment group and body system (or System Organ Class [SOC] and preferred term) overall, by severity, and by relationship to study drug using subject counts and percent. Those AEs with missing onset dates or missing severity will be included as treatment-emergent. If an AE is reported more than once during the double-blind study phase, the greatest severity and the worst-case attribution will be used for presentation in tables.

Deaths, SAEs, and AEs causing discontinuation of study participation and/or study treatment will be tabulated by treatment group with subject counts and percent. Adverse events for individual subjects will be listed, along with information regarding onset, duration, severity, and relationship to study drug.

9.9.2 Other Safety Endpoints

Baseline physical examination findings and clinical laboratory data will be summarized. Vital signs and weight will be summarized using descriptive statistics including mean values and change from baseline values, as well as numbers of subjects with values outside limits of the normal range at each time point.

Prior/concomitant medications will be coded using the World Health Organization (WHO) Drug Dictionary (WHODrug), Version December 2010 or later, and summarized by drug class with subject counts and percent.

9.10 Interim Analysis

A blinded interim analysis is planned for both co-primary endpoints in this study to evaluate the sample size assumptions as follows:

1. Co-primary endpoint change from baseline in the 7-day average CSNS (instantaneous AM) to assess the variance.
2. Co-primary endpoint change from baseline to Week 24/ET APOV to assess variance.

This interim analysis is planned to occur when at least 50% of subjects have reached Week 24/ET endpoint for APOV. At this time it is anticipated that at least 75% of subjects will have reached the Week 4 endpoint for CSNS. The complete details of this interim analysis is provided in the IA-SAP.

10 DATA QUALITY ASSURANCE

10.1 Case Report Forms

Clinical data will be entered on CRFs for transmission to the Sponsor or their designee. Data on CRFs must correspond to and be supported by source documentation maintained at the study center. All study forms and records transmitted to the Sponsor or their designee must carry only coded identifiers such that personally identifying information is not transmitted.

Any changes made to data after collection will be made through the use of Data Clarification Forms (DCF). Data reported on the CRFs, which are derived from source documents, should be consistent with the source documents or the discrepancies should be explained. CRFs will be considered complete when all missing and/or incorrect data have been resolved.

10.2 Source Documents

Source documents are considered to be all information in original records and certified copies of original records of clinical findings, observations, data, or other activities in a clinical study necessary for the reconstruction and evaluation of the study.

The investigator agrees to allow inspections of the study site and any source documentation, by clinical research and audit personnel from the Sponsor or their designee, and external auditors or representatives of regulatory authorities. Direct access to the subject's medical/clinical records is necessary to verify and corroborate the data recorded on the CRFs.

10.3 Record Retention

Study records and source documents need to be preserved for at least 15 years after the completion or discontinuation of/withdrawal from the study or 2 years after the last approval of a marketing application in an ICH region, whichever is the longer time period.

11 QUALITY CONTROL AND QUALITY ASSURANCE

The Sponsor or their designee will perform the quality assurance and quality control activities of this study; however, responsibility for the accuracy, completeness, and reliability of the study data presented to the Sponsor lies with the investigator generating the data.

The Sponsor may arrange audits as part of the implementation of quality assurance to ensure that the study is being conducted in compliance with the protocol, Standard Operating Procedures, GCP, and all applicable regulatory requirements. Audits will be independent of and separate from the routine monitoring and quality control functions.

12 REGULATORY AND ETHICAL CONSIDERATIONS

12.1 Ethical Conduct of the Study

This study will be conducted in accordance with the accepted version of the Declaration of Helsinki and/or all relevant federal regulations, as set forth in Parts 50, 56, 312, Subpart D, of Title 21 of the Code of Federal Regulations (CFR), and in compliance with GCP guidelines.

Institutional Review Boards will review and approve this protocol and informed consent. All subjects are required to give written informed consent prior to participation in the study. This study will be performed in accordance with GCP by qualified investigators. The study specifically incorporated the following features:

- multi-center, placebo controlled, double-blind, study design
- prospectively stated objectives and analytical plan;
- accepted, pre-specified outcome measures for safety and efficacy;
- site initiation meeting prior to study start and a detailed protocol to promote consistency across sites; and
- compliance with GCP, with assessment via regular monitoring.

Quality assurance procedures will be performed at study sites and during data management to assure that safety and efficacy data are adequate and well documented.

